12.1.5 Suspected transmission of an infectious agent via a medicinal product

For the purposes of reporting, any suspected transmission of an infectious agent via a medicinal product should be considered as an SAE; such cases must be reported immediately, recorded in the AE module of the eCRF, and followed as any other SAE. Any organism, virus, or infectious particle (eg, prion protein transmitting transmissible spongiform encephalopathy), pathogenic or nonpathogenic, is considered an infectious agent.

12.1.6 Overdose of investigational medicinal product

Excessive dosing (beyond that prescribed in the protocol and including overdose) should be recorded in the eCRF. Any SAE or nonserious AE associated with excessive dosing must be followed as any other SAE or nonserious AE. These events are only considered AEs or SAEs if there are associated clinical signs and symptoms or if the act of taking the excess medicine itself is an AE or SAE (eg, suicide attempt).

12.1.7 Safety signal detection

Selected data from this study will be reviewed periodically to detect as early as possible any safety concern(s) related to the IMP so that Investigators, clinical study subjects, regulatory authorities, and IRBs/IECs will be informed appropriately and as early as possible.

The Study Physician or medically qualified designee/equivalent will conduct an ongoing review of SAEs and perform ongoing SAE reconciliations in collaboration with the PS representative.

As appropriate for the stage of development and accumulated experience with the IMP, medically qualified personnel at UCB may identify additional safety measures (eg, AEs, vital signs, laboratory or ECG results) for which data will be periodically reviewed during the course of the study.

In addition, an independent Data Monitoring Committee (DMC) will periodically review and monitor the safety data from this study and advise UCB. The DMC membership includes clinicians knowledgeable about the disease or the treatment. All members have experience and expertise in clinical studies. Board members may not participate in the study as principal or co-Investigators, or as study subject care physicians. The duration of membership for the DMC will be inclusive of planned analyses for PA0011. The DMC may also be asked to provide a review of final study results, as deemed appropriate. The DMC procedures will ensure that data remain blind to the study team and Investigators at all times throughout the conduct of the study. The detailed role, scope, responsibilities, and complete procedures, as well as the identity of the DMC members, will be described in a separate charter document. A Cardiovascular Adjudication Committee and a Neuropsychiatric Adjudication Committee will be in place for this study. Specific procedures will be outlined in the charters, which will be developed by the committee members.

12.2 Laboratory measurements

Clinical laboratory assessments consist of serum biochemistry, hematology, urinalysis and pregnancy tests (serum or urine) (Table 5-1). A centralized laboratory will be used to supply all laboratory test supplies and analyze all blood and urine samples for hematology and biochemistry. Any unscheduled laboratory testing should also be collected using the central

laboratory (with the exception of urgent safety laboratory measurements which should be performed locally and centrally simultaneously). Testing to rule out hepatitis B, hepatitis C, and HIV will be performed at Screening. Rheumatoid factor and anti-CCP testing will also be performed at Screening. Testing of HLA-B27 will be performed at Baseline.

Specific details regarding the handling and processing of serum biochemistry and hematology, are provided in the study laboratory manuals.

Laboratory parameters to be measured are presented in [Table 12-2](#).

PUBLIC COPY
This document cannot be used to support any marketing authorization application and any extensions or variations thereof.

Table 12-2: Laboratory measurements

Hematology	Biochemistry	Urinalysis
Basophils	Calcium	pH
Eosinophils	Chloride	Albumin (protein)
Lymphocytes	Magnesium	Glucose
Monocytes	Potassium	Blood
Neutrophils	Sodium	Leukocyte esterase
Hematocrit	Glucose	Nitrite
Hemoglobin	BUN	Urine dipstick for pregnancy testing ^b
MCH	Creatinine	Urine drug screen ^c
MCHC	hs-CRP	
MCV	AST	
Platelet count	ALT	
RBC count	GGT	
WBC count	ALP	
	Total bilirubin	
	Triglycerides ^a	
	Cholesterol ^a	
	HDL cholesterol ^a	
	LDL cholesterol ^a	
	LDH	
	Serum pregnancy testing ^b	

ALP=alkaline phosphatase; ALT=alanine aminotransferase; AST=aspartate aminotransferase; BUN=blood urea nitrogen; ET=early termination; GGT=gamma-glutamyltransferase; HDL=high density lipoprotein; hs-CRP=high sensitivity C-reactive protein; IMP=investigational medicinal product; LDH=lactate dehydrogenase; LDL=low density lipoprotein; MCH=mean corpuscular hemoglobin; MCHC=mean corpuscular hemoglobin concentration; MCV=mean corpuscular volume; RBC=red blood cell; SFU=Safety Follow-Up; WBC=white blood cell

^a Biochemistry will include triglycerides, cholesterol, HDL cholesterol, and LDL cholesterol at Baseline, Week 16, and at the ET Visit.

^b Pregnancy testing will consist of serum testing at the Screening Visit for all women of childbearing potential. The pregnancy test will be urine at all other visits.

^c Urine drug screen will be performed at the Screening Visit.

12.2.1 Evaluation of potential drug-induced liver injury

The PDILI IMP discontinuation criteria for this study are provided in [Section 6.3.1](#), with the accompanying required follow-up investigation and monitoring detailed below. All PDILI events must be reported as AEs and PDILI events meeting SAE criteria should be reported to the study

site and Sponsor within 24 hours of learning of their occurrence. Any PDILI event that meets the criterion for potential Hy's Law must be reported within 24 hours of learning of their occurrence as an AE of special interest (see [Section 12.1.1.3](#)), and, if applicable, also reported as an SAE (see [Section 12.1.1.2](#)).

Evaluation of PDILI consists of the diagnostic testing and continued monitoring included in [Table 12-3](#) (specific tests dependent on laboratory results and corresponding symptoms) and consultation with a local hepatologist (if applicable; discussed in [Section 12.2.1.1](#)). The local hepatologist is the expert usually consulted by the treating physician for assessment and management of potential hepatic disease. This would usually be a hepatologist but may be a gastroenterologist. Additional investigation and monitoring may be required and adapted based on the diagnosis after the cause of the liver injury/abnormality is confirmed (details in [Section 12.2.1.4](#)).

The results of all monitoring, including laboratory testing and other testing, should be made available to the study site and Sponsor.

All initial tests resulting in abnormal hepatic laboratory values need to be repeated, but appropriate medical action must not be delayed waiting for the repeat result.

If tests are done locally for more rapid results, a concurrent sample should also be sent to the central laboratory whenever possible. Medical care decisions are to be made initially using the most rapidly available results and a conservative approach must be taken if the results from the 2 laboratory tests are significantly different. Data from the local and central laboratory are to be recorded on the applicable eCRF pages.

When IMP is discontinued, all concomitant medications and herbal supplements that are not medically necessary should also be discontinued. In these cases, the Investigator should also consider dose reduction for medically necessary concomitant medication and consider changing any medically required concomitant medication known to be hepatotoxic to a suitable alternative.

When IMP is stopped due to PDILI (as described in [Section 6.3.1](#)), IMP must be permanently discontinued unless a subsequent alternative diagnosis fully explains the hepatic findings. If a subsequent alternative diagnosis fully explains the hepatic findings, and the requirements provided in [Section 12.2.1.2.1](#) are met, rechallenge with IMP may be appropriate.

The approach to investigate PDILI is summarized in [Table 12-3](#).

Table 12–3: Required investigations and follow-up for PDILI

Laboratory value			Immediate		Follow up	
ALT or AST	Total bilirubin	Symptoms ^a of hepatitis of hypersensitivity	Consultation requirements	Actions	Testing	Evaluation
≥3xULN	≥2xULN ^b	NA	Hepatology consult ^c Medical Monitor must be notified within 24 hours (eg, by laboratory alert) and subject discussed with Medical Monitor ASAP.	Immediate IMP discontinuation. ^d	Essential: Must have repeat liver chemistry values and additional testing completed ASAP (see Section 12.2.1.3); recommended to occur at the site with HCP.	Monitoring of liver chemistry values at least twice per week until values normalize, stabilize, or return to within baseline values. ^e
≥3xULN	NA	Yes				
≥8xULN	NA	NA				

Table 12–3: Required investigations and follow-up for PDILI

Laboratory value			Immediate		Follow up	
ALT or AST	Total bilirubin	Symptoms ^a of hepatitis of hypersensitivity	Consultation requirements	Actions	Testing	Evaluation
≥5xULN (and ≥2x baseline) and <8xULN	<2xULN	No	
Discussion with Medical Monitor required.
 
Consider need for hepatology consult if there is no evidence of resolution (see Follow up requirements).^c
	
Further investigation – immediate IMP discontinuation not required (see Section 12.2.1.2).
 
IMP discontinuation required if any of the following occur:
 
 • Subject cannot comply with monitoring schedule. • Liver chemistry values continue to increase. • Liver chemistry values remain ≥5xULN (and ≥2x baseline) after 4 weeks of monitoring without evidence of resolution. 	
Essential: Every attempt must be made to have repeat liver chemistry values and additional testing completed within 48 hours at the site with HCP (see Section 12.2.1.3).
	
Monitoring of liver chemistry values at least twice per week for 2 weeks.^c
 
 • Immediate IMP discontinuation required if liver chemistry values continue to increase. 
After 2 weeks of monitoring liver chemistry values:
 
 • ALT or AST remains ≥5xULN <8xULN, IMP should be temporarily withheld and subject should undergo repeat test in 2 weeks. • Continue IMP if ALT or AST values <5xULN; continue to monitor at least twice per week until values normalize, stabilize, or return to within baseline values.

Table 12–3: Required investigations and follow-up for PDILI

Laboratory value			Immediate		Follow up	
ALT or AST	Total bilirubin	Symptoms ^a of hepatitis of hypersensitivity	Consultation requirements	Actions	Testing	Evaluation
						
 If ALT or AST remains $\geq 5 \times \text{ULN}$ after second re-test, immediate IMP discontinuation required. Continue to monitor until values normalize, stabilize, or return to within baseline values. ^e

ALP=alkaline phosphatase; ALT=alanine aminotransferase; ASAP=as soon as possible; AST=aspartate aminotransferase; HCP=healthcare practitioner; IMP=investigational medicinal product; NA=not applicable; PDILI=potential drug-induced liver injury; ULN=upper limit of normal

^a Hepatitis symptoms include fatigue, nausea, vomiting, and right upper quadrant pain or tenderness; hypersensitivity symptoms include eosinophilia (>5%), rash, and fever (without clear alternative cause).

^b If the subject also has $\geq 2 \times \text{ULN}$ ALP, the possibility of an indication of biliary obstruction should be discussed with the Medical Monitor.

^c Details provided in Section 12.2.1.1. The local hepatologist is the expert usually consulted by the treating physician for assessment and management of potential hepatic disease. This would usually be a hepatologist but may be a gastroenterologist.

^d Details are provided in Section 12.2.1.2.

^e Unless an alternative monitoring schedule is agreed by the Investigator and UCB responsible physician. Determination of stabilization is at the discretion of the Investigator in consultation with the hepatologist (as applicable) and UCB responsible physician, as needed.

12.2.1.1 Consultation with Medical Monitor and local hepatologist

Potential drug-induced liver injury events require notification of the Medical Monitor within 24 hours (eg, by laboratory alert), and the subject must be discussed with the Medical Monitor as soon as possible. If required, the subject must also be discussed with the local hepatologist. The local hepatologist is the expert usually consulted by the treating physician for assessment and management of potential hepatic disease. This would usually be a hepatologist but may be a gastroenterologist. If determined necessary, this discussion should be followed by a full hepatology assessment (see [Section 12.2.1.3](#)) and SAE report (if applicable).

12.2.1.2 Immediate action: determination of IMP discontinuation

All PDILI events require immediate action, testing, and monitoring.

The immediate action is dependent on the laboratory values and symptoms of hepatitis or hypersensitivity and ranges from continuation of IMP (followed by immediate investigation) to immediate and permanent discontinuation (see [Section 6.3.1](#) and [Table 12-3](#) for details).

When IMP is discontinued, all concomitant medications and herbal supplements that are not medically necessary should also be discontinued. The Investigator should also consider dose reduction for medically necessary concomitant medication and consider changing any medically required concomitant medication known to be hepatotoxic to a suitable alternative.

12.2.1.2.1 IMP restart/rechallenge

Subjects who are immediately discontinued from IMP due to having met certain criteria for PDILI (as described in [Section 6.3.1](#) and [Table 12-3](#)), but for whom an alternative diagnosis is confirmed, ie, drug-induced liver injury is excluded, can rarely restart IMP. Rechallenge with IMP can occur only if ALL of the following requirements are met at the time of the rechallenge:

- The results of additional testing and monitoring described in [Section 12.2.1.3](#) and [Section 12.2.1.4](#) confirm a nondrug-related cause for the abnormal hepatic laboratory parameters and any associated symptoms (ie, a subsequent alternative diagnosis fully explains the hepatic findings).
- No alternative treatment options are available to the subject.
- The subject has shown clear therapeutic benefit from the IMP.
- Subject's ALT or AST elevations do not exceed $\geq 3xULN$.
- Subject's total bilirubin is $< 1.5xULN$.
- Subject has no signs or symptoms of hypersensitivity.
- The rechallenge is approved by the UCB responsible physician and a hepatologist. The hepatologist must be external to UCB. It is recommended that the hepatologist be a local hepatology expert or the hepatologist treating the subject.
- Subject agrees to the investigator-recommended monitoring plan and understands their individual benefit/risk for restarting IMP and this is adequately documented.

12.2.1.3 Testing: identification/exclusion of alternative etiology

The measurements and additional information required for the assessment of PDILI events when there is a reasonable possibility that they may have been caused by the IMP are detailed in [Table 12-4](#) (laboratory measurements) and [Table 12-5](#) (additional information). Results of the laboratory measurements and information collected are to be submitted to the Sponsor on the corresponding eCRF. If the medical history of the subject indicates a requirement for other assessments not included below, these additional assessments should be completed and submitted, as applicable.

All blood samples should be stored, if possible. If tests are done locally for more rapid results, a concurrent sample must also be sent to the central laboratory.

PUBLIC COPY
This document cannot be used to support any marketing authorization application and any extensions or variations thereof.

The following measurements are to be assessed:

Table 12-4: PDILI laboratory measurements

Virology-related	Hepatitis A IgM antibody
	HBsAg
	Hepatitis E IgM antibody
	HBcAb-IgM
	Hepatitis C RNA
	Cytomegalovirus IgM antibody
	Epstein-Barr viral capsid antigen IgM antibody (if unavailable, obtain heterophile antibody or monospot testing)
Immunology	Anti-nuclear antibody (qualitative and quantitative)
	Anti-smooth muscle antibody (qualitative and quantitative)
	Type 1 anti-liver kidney microsomal antibodies (qualitative and quantitative)
Hematology	Eosinophil count
Urinalysis	Toxicology screen ^a
Chemistry	Amylase
	Sodium, potassium, chloride, glucose, BUN, creatinine
	Total bilirubin, ALP, AST, ALT, GGT, total cholesterol, albumin
	If total bilirubin $\geq 1.5 \times \text{ULN}$, obtain fractionated bilirubin to obtain % direct bilirubin
	Serum CPK and LDH to evaluate possible muscle injury causing transaminase elevation
Additional	Prothrombin time/INR ^b
	Serum pregnancy test
	PK sample

ALT=alanine aminotransferase; CPK=creatine phosphokinase; HBcAb-IgM=hepatitis B core antibody-IgM; HBsAg=hepatitis B surface antigen; IgM=immunoglobulin M; INR=international normalized ratio; LDH=lactate dehydrogenase; PDILI=potential drug-induced liver injury; PK=pharmacokinetic; RNA=ribonucleic acid; ULN=upper limit of normal

^a For detecting substances (ie, amphetamines, benzodiazepines, opioids, marijuana, cocaine, phencyclidine, and tricyclic antidepressants), additional tests may be performed based on the Investigator's medical judgment and subject's history.

^b Measured only for subjects with ALT $> 8 \times \text{ULN}$, elevations in total bilirubin, and symptoms of hepatitis or hypersensitivity. Hepatitis symptoms include fatigue, nausea, vomiting, and right upper quadrant pain or tenderness; hypersensitivity symptoms include eosinophilia ($> 5\%$), rash, and fever (without clear alternative cause).

Additional information to be collected is presented in [Table 12-5](#).

Table 12-5: PDILI information to be collected

New or updated information
Concomitant prescription and over-the-counter medications (eg, acetaminophen, herbal remedies, vitamins); dosages and dates should be included.
Pertinent medical history, including the following: 
 • History of liver disease (eg, autoimmune hepatitis, nonalcoholic steatohepatitis or other “fatty liver disease”) • Adverse reactions to drugs • Allergies • Relevant family history or inheritable disorders (eg, Gilbert’s syndrome, alpha-1 antitrypsin deficiency) • Recent travel • Progression of malignancy involving the liver (Note: Metastatic disease to the liver, by itself, should not be used as an explanation for significant AST and/or ALT elevations.)
The appearance or worsening of clinical symptoms of hepatitis or hypersensitivity (eg, fatigue, nausea, vomiting, right upper quadrant pain or tenderness, decreased appetite, abdominal pain, jaundice, fever, or rash)
Recent clinically significant hypotension or hypoxemia with compromised cardiopulmonary function
Alcohol and illicit drug use
Results of liver imaging or liver biopsy, if done
Results of any specialist or hepatology consult, if done
Any postmortem/pathology reports

ALT=alanine aminotransferase; AST=aspartate aminotransferase; PDILI=potential drug-induced liver injury

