6.3.1 Potential drug-induced liver injury IMP discontinuation criteria

Subjects with potential drug-induced liver injury (PDILI) must be assessed to determine if IMP must be discontinued. In addition, all concomitant medications and herbal supplements that are not medically necessary should also be discontinued.

The PDILI criteria below require immediate discontinuation of IMP:

- Subjects with either of the following:
 - ALT or AST $\geq 8xULN$
 - ALT or AST $\geq 3xULN$ and coexisting total bilirubin $\geq 2xULN$
- - Subjects with ALT or AST $\geq 3xULN$ who exhibit temporally associated symptoms of hepatitis or hypersensitivity. Hepatitis symptoms include fatigue, nausea, vomiting, right upper quadrant pain or tenderness. Hypersensitivity symptoms include fever (without clear alternative cause), rash, or eosinophilia (ie, $>5\%$).

If a nondrug-related cause for the symptoms can be confirmed, these subjects may resume IMP administration after discussion with the responsible UCB physician, but only when the requirements for rechallenge with IMP as provided in [Section 12.2.1.2.1](#) are followed.

The PDILI criterion below allows for subjects to continue on IMP at the discretion of the Investigator.

- Subjects with ALT or AST $\geq 5xULN$ and $<8xULN$, total bilirubin $<2xULN$, and no eosinophilia (ie, $\leq 5\%$), with no fever, rash, or symptoms of hepatitis (eg, fatigue, nausea, vomiting, right upper quadrant pain or tenderness).

Evaluation of PDILI must be initiated as described in [Section 12.2.1](#) with repeat tests performed in 2 weeks. Upon retest, if ALT or AST values have reduced to $<5xULN$, the subject can continue with the study. However, if ALT or AST remains $\geq 5xULN$ $<8xULN$ after retest, IMP should be temporarily withheld and subject should undergo a repeat test in 2 weeks. The subject will continue to be monitored at least twice per week until values normalize, stabilize, or return to within baseline values. If ALT or AST values remain $\geq 5xULN$ even after the second retest, then the subject should be permanently withdrawn from the study and should be followed for possible PDILI.

If subjects are unable to comply with the applicable monitoring schedule, IMP must be discontinued immediately.

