12.1.1.3 Adverse events of special interest

An AE of special interest is any AE that a regulatory authority has mandated be reported on an expedited basis, regardless of the seriousness, expectedness, or relatedness of the AE to the administration of a UCB product/compound.

Potential Hy’s Law, defined as $\geq 3 \times \text{ULN}$ ALT or AST with coexisting $\geq 2 \times \text{ULN}$ total bilirubin in the absence of $\geq 2 \times \text{ULN}$ ALP, with no alternative explanation for the biochemical abnormality, must ALWAYS be reported to UCB as an AE of special interest (ie, without waiting for any additional etiologic investigations to have been concluded). Follow-up information should then be reported if an alternative etiology is identified during investigation and monitoring of the subject.

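### Table 12-4 footnote b asks for PT/INR only when three liver signals coincide, so no single immediate-stop criterion, including the potential Hy's Law pattern, calls for it

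*Protocol*

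**What the plan says.** Section 12.2.1.3 introduces Tables 12-4 and 12-5 as "The measurements and additional information required for the assessment of PDILI events", where the study drug may reasonably be the cause. Table 12-4 lists "Prothrombin time/INR" under its additional tests and attaches footnote b. That footnote says the test is "Measured only for subjects with ALT" above 8xULN, "elevations in total bilirubin, and symptoms of hepatitis or hypersensitivity".

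Section 6.3.1 opens its stopping rules with "The PDILI criteria below require immediate discontinuation of IMP" and gives three routes:

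- ALT or AST ≥8xULN;
- ALT or AST ≥3xULN with total bilirubin ≥2xULN;
- ALT or AST ≥3xULN with temporally associated symptoms of hepatitis or hypersensitivity.

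Table 12-3 repeats these as three rows and marks the elements that a row does not use as not applicable. For all three rows the follow-up testing is classed as essential: "Must have repeat liver chemistry values and additional testing completed ASAP", with a pointer to Section 12.2.1.3.

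Section 12.1.1.3 defines potential Hy's Law as ALT or AST ≥3xULN with total bilirubin ≥2xULN and without ALP ≥2xULN. Such a case, "with no alternative explanation for the biochemical abnormality, must ALWAYS be reported to UCB as an AE of special interest".

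**The concern.** The same kinds of signal (high transaminase, raised bilirubin, symptoms) are alternatives in the stopping rules but are joined by *and*, after *only*, in the INR footnote. A subject can therefore meet a stopping rule, be sent to the essential work-up, and fall outside the INR condition.

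INR measures liver synthetic function. The gap matters most for the potential Hy's Law pattern, which the protocol treats as its most urgent hepatic signal and which requires neither ALT above 8xULN nor symptoms. The routine laboratory list (Table 12-2) contains no PT or INR and no other section asks for it, so footnote b alone decides whether it is in the required panel. Two smaller mismatches widen the gap: the footnote names ALT but not AST, and uses >8xULN where the stopping rule uses ≥8xULN.

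**Working it through.** The plan gives no figure to reproduce; this is a check of logic.

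**Inputs**

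- INR condition (Table 12-4, footnote b): ALT >8xULN *and* bilirubin elevated (taken as >ULN, since the footnote gives no threshold) *and* symptoms.
- Stop criteria (Section 6.3.1, Table 12-3): (1) ALT or AST ≥8xULN; (2) ALT or AST ≥3xULN with bilirubin ≥2xULN; (3) ALT or AST ≥3xULN with symptoms.

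**Is any stop criterion sufficient for INR?**

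| Criterion met | ALT >8xULN guaranteed? | Raised bilirubin guaranteed? | Symptoms guaranteed? | Sufficient for INR? |
|---|---|---|---|---|
| (1) | No (AST may drive it, or ALT may be exactly 8) | No | No | No |
| (2) | No | Yes | No | No |
| (3) | No | No | Yes | No |

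Result: 0 of 3.

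**Worked case.** ALT 5xULN, bilirubin 3xULN, ALP <2xULN, no alternative explanation, no symptoms. Criterion (2) is met because 5 ≥ 3 and 3 ≥ 2, and the Section 12.1.1.3 definition is met. Footnote b is not, because 5 is not above 8 and there are no symptoms. Adding symptoms does not change the answer, since the ALT condition still fails.

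**Cross-classification.** ALT in 2 bands (3 to <8, >8xULN), bilirubin in 3 (≤ULN, >ULN to <2xULN, ≥2xULN), symptoms yes or no: 2 × 3 × 2 = 12 profiles.

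- Meeting a stop criterion: all 3 × 2 = 6 profiles with ALT >8xULN. In the lower ALT band, 2 have bilirubin ≥2xULN and 2 more have lower bilirubin with symptoms. Total 6 + 2 + 2 = 10.
- Of these 10, footnote b calls for INR where ALT >8xULN, bilirubin is in either raised band and symptoms are present: 2.
- With bilirubin ≥2xULN: 2 × 2 = 4 profiles, with INR in 1.

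**Finer grid, including AST and ALT exactly 8xULN.** Values in xULN: ALT 1, 3, 5, 7.9, 8, 8.1, 10; AST 1, 3, 5, 8, 10; bilirubin 0.8, 1.1, 1.5, 2, 3; symptoms yes or no. This gives 7 × 5 × 5 × 2 = 350 points.

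| Stop criterion | Points meeting it | INR, elements joined by *and* | INR, elements as alternatives |
|---|---|---|---|
| ALT or AST ≥8xULN | 230 | 40 | 217 |
| ≥3xULN with bilirubin ≥2xULN | 136 | 20 | 136 |
| ≥3xULN with symptoms | 170 | 40 | 170 |

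Reading the elements as alternatives closes the second and third rows but leaves 230 − 217 = 13 points uncovered in the first. All 13 have normal bilirubin and no symptoms, and either AST ≥8xULN with ALT not above 8xULN, or ALT exactly 8xULN. Replacing *and* with *or* is therefore not a complete repair.

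**The case against.** The strongest reply is that footnote b is shorthand. Its three elements resemble the three stop rows of Table 12-3, bilirubin carries no threshold, and a phrase of the form *subjects with A, B, and C* can list three groups. On that reading the Hy's Law gap disappears. This is possible, but it strains *only* followed by *and*, and sites should not have to guess. Even then AST and the boundary at 8xULN remain wrong.

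Second, Section 12.2.1 says the tests depend on laboratory results and symptoms, so tailoring may be deliberate; Section 12.2.1.3 is aimed at finding a cause; and Table 12-4 requires albumin, another though slower synthetic marker, without condition. This is fair, but it does not explain confining INR to the overlap of all three signals.

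Third, affected subjects are closely managed: study drug stops at once, a hepatology consult is required, the Medical Monitor is told within 24 hours, and liver chemistry is repeated at least twice weekly. A hepatologist may well order INR. That stands, and it limits the consequence. These provisions permit INR but do not require it.

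Fourth, no stop, reporting or rechallenge rule uses an INR threshold. That also stands. The panel still counts for something, because Section 12.2.1.2.1 makes the Section 12.2.1.3 results part of the evidence for rechallenge.

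Last, the profile counts depend on the bands chosen and have no clinical weight. Agreed; the result that does not depend on banding is that none of the three criteria is sufficient.

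**Conclusion.** The point holds. As worded, footnote b leaves INR out of the required work-up for any subject stopped on a single liver criterion, including a potential Hy's Law case without both ALT above 8xULN and symptoms. The size is 0 of 3 stop criteria sufficient for INR, and INR in 2 of 10 stop-qualifying profiles, or 1 of 4 with bilirubin ≥2xULN. The profile counts are unweighted, and the protocol gives no frequencies from which to estimate how many subjects would be affected.

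The conclusion rests on reading *and* literally. Under the looser reading the gap shrinks to AST-driven cases and ALT exactly 8xULN, and the footnote still needs rewording. Efficacy analyses, type I error and power are untouched, and nobody would be dosed longer or reported later because of it. It is a low-cost safety correction that should be made.

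**What to change.** Reword footnote b so that PT/INR is measured in every subject who meets any immediate-discontinuation criterion of Section 6.3.1 and Table 12-3: ALT or AST ≥8xULN; or ALT or AST ≥3xULN with total bilirubin ≥2xULN; or ALT or AST ≥3xULN with symptoms of hepatitis or hypersensitivity. This settles the *and/or* question, adds AST, aligns the boundary at 8xULN and gives bilirubin a threshold. INR stays conditional for the milder Table 12-3 row (5 to <8xULN, no symptoms), where study drug may continue.

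Check the laboratory manual, which is not available here, and align it if it repeats the condition. The cost is one footnote, any matching manual text, and a few additional INR tests in rare cases. No stopping or reporting decision changes.
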